## 3 Study Design

### 3.1 Overview of Study Design

This is a Phase 2, multicenter, open-label, single-arm study to evaluate the antitumor activity, safety, and pharmacology of MEDI-575 in adult subjects with first recurrence of GBM.

Approximately 55 subjects will be enrolled to determine the preliminary efficacy profile of MEDI-575 in the treatment of subjects with first recurrence of GBM. Subjects will receive MEDI-575 as a 60-minute IV infusion on Day 1 every 21 days until disease progression, initiation of alternative anticancer therapy, unacceptable toxicity, or other reasons for subject withdrawal (see Section 4.2.3) (Figure 3.1-1). In Cycle 2 and beyond, a dose can be delayed up to 7 days for unavoidable scheduling issues. MEDI-575 may be withheld for up to 21 days until resolution to  $\leq$  Grade 1 toxicity after agreement with the sponsor. The primary assessment of antitumor activity is PFS-6; progression will be determined using *Updated Response Assessment Criteria of High Grade Gliomas- Neuro-Oncology Working Group v.1* (see Appendix 5) (Wen et al, 2010). Approximately 15 investigational sites in the United States (USA) will participate in this study. Subjects who receive any amount of MEDI-575 and proceed to subsequent surgery as therapy for GBM (at second recurrence/disease progression) will be requested to allow use of surgically resected tissue for analysis of intratumoral levels of MEDI-575.

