#### **4.2.3 Withdrawal Criteria**

An individual subject will not receive further treatment if any of the following occur in the subject in question:

- 1) Withdrawal of consent or lost to follow-up
- 2) Adverse event that, in the opinion of the investigator or medical monitor, contraindicates further dosing
- 3) Subject is determined to have met 1 or more of the exclusion criteria for study participation
- 4) Pregnancy

**Withdrawal of consent:** If consent is withdrawn, the subject will not receive any further treatment or further study observation. Note that the subject may need to undergo additional tests or tapering of treatment to withdraw safely.

**Lost to follow-up:** Subjects will be considered lost-to-follow-up only if no contact has been established by the time the study is completed such that there is insufficient information to determine the subject's status at the end of study (defined as 9 months from the date the last subject is entered into the trial or when the sponsor stops the study).

- Note: Subjects refusing to return to the site or to continue participation in the study should be documented as “withdrawal of consent” rather than “lost to follow-up.” Investigators should document attempts to re-establish contact with missing subjects throughout the study period. If contact with a missing subject is re-established, the subject should not be considered lost-to-follow-up and any evaluations should resume according to the protocol

**Permanent discontinuation of treatment:** Subjects who are permanently discontinued from further receipt of treatment, regardless of the reason (withdrawal of consent, due to an AE, other), will be identified as having permanently discontinued treatment. Subjects who permanently discontinue treatment may either be considered to have completed the study or not to have completed the study (see Section 4.6).

Subjects who are permanently discontinued from receiving treatment will be followed for safety through 90 days after the last dose of treatment, including the collection of any protocol-specified blood or urine specimens, unless the subject withdraws consent, is lost to follow-up, or has enrolled in another clinical study.

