### **5.2.4 Every 2 Cycles, Beginning with Cycle 3**

The following evaluations will be performed every 2 cycles (ie, every 6 weeks) unless otherwise indicated, beginning at Cycle 3 (eg, Cycle 3, Cycle 5, etc.)

- 1) Assess for disease response:
  - MRI scan (within 7 days prior to start of cycle)

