### **5.2.6.3 Every 3 Months (Plus or Minus 14 Days) After Last Treatment**

The following evaluations will be performed every 3 months ( $\pm$  14 days) after the last treatment as specified (for subjects who discontinue treatment due to reasons other than disease progression or initiation of alternative anticancer therapy, these evaluations will be performed until documentation of disease progression, initiation of alternative anticancer therapy, or the end of study [defined as 9 months post the date the last subject is entered on the trial or when sponsor stops the study]):

- 1) Evaluation of disease
  - MRI scan
  - Focused physical examination
  - ECOG performance status

- 2) Blood collection for anti-MEDI-575 antibodies (3-month post visit only)
- 3) Survival status and subsequent anticancer therapy must be collected in every subject regardless of the reason for treatment discontinuation. Assessment can be either performed on a clinic visit or telephone contact until death or the end of the study

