### **5.3.7 Disease Evaluation and Methods**

Tumor measurements and assessments will be based on *Updated Response Assessment Criteria of High Grade Gliomas- Neuro-Oncology Working Group* (Wen et al, 2010) (see [Appendix 4](#) and [Appendix 5](#)) and will be performed as specified in [Table 5.2-1](#) and [Table 5.2-2](#). Tumor assessments include an MRI scan of the brain. Additional tumor assessments may be performed at the discretion of the investigator or according to institutional practice. In subjects who achieve a complete or partial response to treatment, tumor measurements will be repeated at least 4 weeks later using the same imaging tests. The same tumor assessment method should be used throughout the treatment period. It is recommended to use the same MRI scanner or one with same magnet strength throughout the assessments.

Blinded central independent imaging review of response and disease progression will be utilized. Details of study-specific procedures for collection and shipment of images will be provided in a separate manual.

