- Progression-free survival will be measured from the start of treatment with MEDI-575 until the documentation of disease progression or death due to any cause, whichever occurs first. Progression-free survival will be censored on the date of last tumor assessment documenting absence of tumor progression for subjects who have no documented progression and are still alive prior to data cutoff, dropout, or the initiation of alternate anticancer treatment. Subjects having no tumor assessments after the start of treatment with MEDI-575 will have PFS censored on the first date of treatment with MEDI-575. Progression-free survival will be evaluated using the Kaplan-Meier method.
- Overall survival will be determined as the time from the start of treatment with MEDI-575 until death. For subjects who are alive at the end of study or lost to follow-up, OS will be censored on the last date when subjects are known to be alive. Overall survival will be evaluated using the Kaplan-Meier method.

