Progression	
Defined by any of the following: <math>\geq 25\%</math> increase in sum of the products of perpendicular diameters of enhancing lesions compared with the smallest tumor measurement obtained either at baseline (if no decrease) or best response, on stable or increasing doses of corticosteroids*; significant increase in T2/FLAIR nonenhancing lesion on stable or increasing doses of corticosteroids compared with baseline scan or best response after initiation of therapy* not caused by comorbid events (eg, radiation therapy, demyelination, ischemic injury, infection, seizures, postoperative changes, or other treatment effects); any new lesion; clear clinical deterioration not attributable to other causes apart from the tumor (eg, seizures, medication adverse effects, complications of therapy, cerebrovascular events, infection, and so on) or changes in corticosteroid dose; failure to return for evaluation as a result of death or deteriorating condition; or clear progression of nonmeasurable disease.

Note: All measurable and nonmeasurable lesions must be assessed using the same techniques as at baseline.

Abbreviations: MRI, magnetic resonance imaging; FLAIR, fluid-attenuated inversion recovery.

\*

Stable doses of corticosteroids include patients not on corticosteroids.

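### PFS sets no limit on the gap between the last MRI and a later death, and does not count or date Appendix 4's non-return through deterioration, so a subject who stops scans before month 6 and dies after it can count as a PFS-6 success

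*Protocol*

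**What the plan says.** Section 7.3.2.1 of the protocol measures PFS from the start of treatment "until the documentation of disease progression or death due to any cause, whichever occurs first". It censors at the last progression-free tumor assessment only "subjects who have no documented progression and are still alive prior to data cutoff, dropout, or the initiation of alternate anticancer treatment". Section 7.3.1 estimates PFS-6 by Kaplan-Meier with a two-sided 90% confidence interval, and section 7.5 calls the study positive if the lower limit is at least 16%.

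Several other places bear on what counts as progression and when it is seen:

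- Section 3.1: "The primary assessment of antitumor activity is PFS-6; progression will be determined using" the RANO criteria, citing Appendix 5. Sections 3.4 and 5.3.7 cite both Appendix 4 and Appendix 5.
- Appendix 4 includes among its progression criteria "failure to return for evaluation as a result of death or deteriorating condition". The summary in Appendix 5 (and Table 5.3.7-1) lists clinical decline but not non-return.
- Section 5.3.7: "Blinded central independent imaging review of response and disease progression will be utilized".
- Section 5.2.4 schedules on-treatment MRI "every 2 cycles (ie, every 6 weeks) unless otherwise indicated, beginning at Cycle 3". Section 5.2.6.3 schedules MRI every 3 months after treatment for subjects who stop for reasons other than progression or new therapy.
- For survival status and subsequent therapy, section 5.2.6.3 adds: "Assessment can be either performed on a clinic visit or telephone contact until death or the end of the study".
- Section 4.2.3: "Subjects refusing to return to the site or to continue participation in the study should be documented as" withdrawal of consent. It reserves loss to follow-up for subjects with whom no contact has been made by study completion.

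**The concern.** Section 7.3.2.1 fixes both the event and the censoring. A death is an event whenever it occurs, and only living, unprogressed subjects are censored at their last scan. Survival continues to be collected by telephone after imaging has stopped, so a late death reaches the database even if months passed without an MRI. If that death falls after month 6, the subject stays in the risk set through month 6 and counts as progression-free there, although nobody observed that status.

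For a subject who stopped coming because of decline, Appendix 4 points to progression at the time of non-return. Nothing carries this into the PFS analysis. Section 7.3.2.1 requires documentation of progression without saying how a non-return is documented, and a central imaging reader has no image to read for that visit. Two analysts could give the same subject opposite primary outcomes.

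For these subjects the error runs only toward success. There is no control arm in which the same error would occur, and the benchmark is a fixed 16%.

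**Working it through.** **1. One subject under each passage.** Suppose the last clear MRI is at week 12 (Cycle 5), later visits are missed because of decline, no consent is withdrawn, no new therapy is started, and death occurs at month 7.

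- Section 7.3.2.1 taken alone: no documented progression, so the event is death at month 7. The subject is progression-free at 6 months.
- Appendix 4: non-return through deterioration is progression. If the subject was still on treatment, the next MRIs were due near weeks 18 and 24, both before month 6. If treatment stopped at week 12, the first 3-monthly MRI is due near week 25 (12 + 13), give or take 2 weeks, so its date is close to month 6.

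**2. The plan's own design figure.** Inputs from section 7.5: n = 50, p0 = 0.16, p1 = 0.30, two-sided alpha 0.1 (z = 1.645).

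Power = Φ[(p1 − p0 − z·√(p0(1−p0)/n)) / √(p1(1−p1)/n)]
= Φ[(0.14 − 1.645 × 0.05185) / 0.06481] = Φ(0.844) = 80.1%, against 80% stated.

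The other rows of Table 7.5-1 come out at 53.1, 70.8, 87.1 and 94.0%, against 55, 72, 86 and 92%, all within 2 points. The design figure is not in question.

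**3. Successes needed with 55 subjects.** Without censoring before month 6, the Kaplan-Meier estimate is x/55. The protocol does not state the interval type, so both are shown.

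| x | PFS-6 | Lower 90% limit, plain | Lower 90% limit, log-log |
|---|---|---|---|
| 13 | 23.6% | 14.2% | 14.9% |
| 14 | 25.5% | 15.8% | 16.4% |
| 15 | 27.3% | 17.4% | 18.0% |

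The rule needs c = 15 (plain) or c = 14 (log-log). One subject is worth 1/55 = 1.8 points.

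**4. False-positive rate if k true failures are counted as successes.** At a true PFS-6 of 16%, the study is positive when true successes + k ≥ c, so the rate is P(Bin(55, 0.16) ≥ c − k).

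| k (assumed) | Plain, c = 15 | Log-log, c = 14 |
|---|---|---|
| 0 | 2.3% | 4.8% |
| 1 | 4.8% | 9.1% |
| 2 | 9.1% | 16.0% |
| 3 | 16.0% | 25.8% |

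**5. A constructed trial.** Assume 55 subjects: 11 scanned clear past month 6; 4 last scanned clear at 2.8 months who die at month 8; and 40 who progress at scans at 1.4, 2.8, 4.1 and 5.5 months (19, 11, 6 and 4 subjects).

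- Event at death (section 7.3.2.1 taken alone): 15/55 = 27.3%, lower limit 17.4% (plain) or 18.0% (log-log). Positive.
- Censored at last MRI: (36/55)(25/36)(15/21)(11/15) = 23.8%, lower limit 13.8% or 14.6%. Not positive.
- Non-return counted as progression: 11/55 = 20.0%, lower limit 11.1% or 12.0%. Not positive.

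With 3 such subjects instead of 4, the log-log result also changes: 14/55 gives a limit of 16.4%, while counting them as progressed gives 12.0%.

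**The case against.** The strongest reply is that the passages can be read together. Sections 3.4 and 5.3.7 adopt Appendix 4, where clear clinical deterioration and non-return through deterioration are both progression. Section 7.3.2.1 takes whichever event comes first, so the example subject has already progressed before death. This stands in part: a reader might infer an outright contradiction, and the text does not support that. What remains is that no passage says how non-return is documented or dated, while progression goes to a central imaging review and the appendix cited for PFS-6 in section 3.1 leaves the criterion out.

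A reader might also infer that Appendix 4 makes every missed MRI progression, or that every subject with lapsed scans becomes a success. Neither follows. Appendix 4 requires death or deterioration as the cause, so a scan missed for logistics is not covered. Subjects who start other therapy are censored at their last clear scan. Refusal to return is recorded as withdrawal of consent, and such subjects are plausibly censored as dropouts, although dropout is not defined for someone who skips MRIs but stays in telephone follow-up.

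There are safeguards too: missed evaluations are to be rescheduled (section 5.2), an MRI is due at treatment discontinuation (5.2.5), and examination and ECOG status are recorded at 30, 60 and 90 days (5.2.6). The telephone option does not replace the MRI. These narrow the route to a false success but do not close it.

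Finally, section 7.1 leaves details to the SAP, and a missed-scan rule is often placed there. Its absence alone would be no finding. But section 7.3.2.1 already fixes the event, the censoring and the case of no post-baseline assessment, so the deferral does not fully dispose of the point.

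**Conclusion.** The point holds in a limited form. Section 7.3.2.1 allows an unlimited interval between the last adequate MRI and a later death, and does not carry Appendix 4's non-return criterion into the PFS event or its date. A subject whose scans stop before month 6 because of decline, who is not withdrawn, starts no new therapy and dies after month 6 can be counted as progression-free at 6 months. The bias is toward success.

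One such subject about doubles the false-positive rate at a true 16%: from 2.3% to 4.8% with the plain interval, or from 4.8% to 9.1% with the log-log interval. This assumes 55 subjects, no other censoring before month 6, and a subject who truly failed. The protocol gives no rate of such lapses, so the range of 1 to 3 is illustrative and not a prediction. A rule based on a set number of consecutive missed scans is a convention on which statisticians differ, and the protocol cannot be faulted for lacking one.

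**What to change.** Add to section 7.3.2.1 that, for PFS and PFS-6, non-return because of death or deterioration is a progression event under Appendix 4 even without an image for central review. Date it at the first scheduled MRI not done, or at death or documented clinical progression if that is earlier. Record the reason for each missed MRI on the CRF.

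As a sensitivity analysis, censor at the last clear MRI those subjects whose event follows scans missed for other reasons.

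The cost is a short addition to the text and one CRF field. PFS-6 may come out slightly lower.

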## 7.2 Analysis Populations

The intent-to treat (ITT) population will include all subjects entered into the study. The ITT population is the primary population for the efficacy analyses and the summary of baseline characteristics.

The evaluable population will include all subjects who received at least 1 dose of MEDI-575 and had at least 1 post-baseline disease assessment. The evaluable subject population will be the secondary population for efficacy analysis.

The safety population will include all subjects who receive at least 1 dose of MEDI-575 and will be used to summarize the safety assessments.

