## 7.3 Endpoints

### 7.3.1 Primary Endpoint

The primary objective of this study is to evaluate the PFS-6 in adult subjects with a first recurrence of GBM who are treated with MEDI-575.

The PFS-6 rate will be summarized and its 2-sided 90% CI will be calculated based on the Kaplan-Meier method ([Kaplan and Meier, 1958](#)).

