#### 7.3.2.1 Secondary Endpoints of Antitumor Activity of MEDI-575

Assessments of other antitumor activities include ORR, TTR, DR, TTP, PFS, and OS. *The Updated Response Assessment Criteria of High Grade Gliomas - Neuro-Oncology Working Group* ([Wen et al, 2010](#)) will be used to determine tumor response.

- Objective response rate is defined as the proportion of subjects with confirmed CR or confirmed PR according to the *Updated Response Assessment Criteria of High*

*Grade Gliomas- Neuro-Oncology Working Group (Wen et al, 2010)*. Confirmed responses are those that persist on repeat imaging studies at least 4 weeks after the initial documentation of response. The 2-sided 90% and 95% CIs of ORR will be estimated using the exact probability method.

- Time to response will be measured from the start of MEDI-575 administration to the first documentation of response (CR or PR) and will only be assessed in subjects who have achieved objective response.
- Duration of response will be defined as the duration from the first documentation of objective response to the first documented disease progression. Duration of response will be censored on the date of last tumor assessment documenting absence of disease progression for subjects who have no documented progression prior to data cutoff, dropout, or the initiation of alternate anticancer treatment. Duration of response will only be evaluated for the subgroup of subjects with an objective response and will be assessed using the Kaplan-Meier method.
- Time to progression will be measured from the start of treatment with MEDI-575 until the documentation of disease progression. Time to progression will be censored on the date of last tumor assessment documenting absence of tumor progression for subjects who have no documented progression prior to data cutoff, dropout, or the initiation of alternate anticancer treatment. Subjects having no tumor assessments after the start of treatment with MEDI-575 will have TTP censored on the first date of treatment with MEDI-575. Time to progression will be evaluated using the Kaplan-Meier method.

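### The PFS definition behind PFS-6 contradicts itself on subjects who die or progress clinically without a post-treatment scan; read literally, it censors them on Day 1 and biases PFS-6 upward

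*Protocol*

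**What the plan says.** Section 7.3.2.1 runs PFS from the start of treatment "until the documentation of disease progression or death due to any cause, whichever occurs first". The next sentence censors at the last progression-free tumor assessment, and only "for subjects who have no documented progression and are still alive prior to data cutoff, dropout, or the initiation of alternate anticancer treatment". The third sentence is: "Subjects having no tumor assessments after the start of treatment with MEDI-575 will have PFS censored on the first date of treatment with MEDI-575". It carries no condition on vital status or progression.

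The TTP definition in the same section ends with the same sentence, "Subjects having no tumor assessments after the start of treatment with MEDI-575 will have TTP censored on the first date of treatment with MEDI-575", although death is not a TTP event.

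For the primary endpoint, Section 7.3.1 says only this: "The PFS-6 rate will be summarized and its 2-sided 90% CI will be calculated based on the Kaplan-Meier method". It does not say what counts as an event or when a subject is censored, so the PFS paragraph in Section 7.3.2.1 is the only definition available.

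Appendix 4 lists clear clinical deterioration as progression, and also "failure to return for evaluation as a result of death or deteriorating condition". Neither needs a scan.

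Sections 5.2.4 and 5.2.5 schedule on-treatment MRI every two cycles from Cycle 3, within the 7 days before the cycle starts, and another MRI at treatment discontinuation.

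**The concern.** The unscanned group is not a random subset. It contains subjects who die, or become too ill to return, before the first MRI, and these are the earliest failures in the trial. Censoring them at time zero removes them from every risk set, so they count neither as failures nor in the denominator. The trial has one arm and is positive if the lower 90% limit for PFS-6 reaches 16% (Section 7.5). No control group shares the bias, and it can only run toward a positive result.

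The two readings put the same subject on opposite sides of the primary analysis. In an open-label trial, that choice should not be made once outcomes are visible.

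**Working it through.** **1. The sentences applied to one case.** Take a subject who dies on Day 25 with no scan since the first dose.
- PFS event sentence: event on Day 25.
- General censoring sentence: not eligible for censoring, because the subject is not alive.
- No-assessment sentence: censored on Day 1.
- Appendix 4: progression, through failure to return because of death.

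Three of the four give a failure. The third, applied as written, gives no information at all.

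**2. Window.** With 21-day cycles and no delay, Cycle 3 Day 1 is Day 1 + 2 x 21 = Day 43. The 7-day window opens on Day 36.

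**3. The plan's own power figure.** With p0 = 0.16, n = 50 and z = 1.645, use power = Phi[(p1 - p0 - z*sqrt(p0(1-p0)/n)) / sqrt(p1(1-p1)/n)]. At p1 = 0.30 this gives 80.1% against the stated 80%. At 25, 28, 32 and 35% it gives 53.1, 70.8, 87.1 and 94.0% against 55, 72, 86 and 92% in Table 7.5-1. The sample size is not the problem.

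**4. Size of the bias.** Let x of n subjects be progression-free at 6 months and k be unscanned early failures, with no other censoring before 6 months. Counted as events, they give an estimate of x/n. Censored at time zero, they give x/(n-k). In expectation the inflation factor is 1/(1-f).

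| f (assumed) | True 16% reads as | True 30% reads as |
|---|---|---|
| 2% | 0.16/0.98 = 16.3% | 0.30/0.98 = 30.6% |
| 5% | 0.16/0.95 = 16.8% | 0.30/0.95 = 31.6% |
| 10% | 0.16/0.90 = 17.8% | 0.30/0.90 = 33.3% |

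**5. Range for f.** The protocol gives no figure. Section 1.4 cites a median OS of about 7 months. If OS were exponential, the share dead by day d would be 1 - 0.5^(d/(30.44 x 7)): 11% at Day 36 and 13% at Day 43, or 6 to 7 of 55. Section 4.2.1 requires ECOG 0 or 1 and a life expectancy of at least 12 weeks, and the discontinuation MRI catches some early failures. Both should lower f, so 2% to 10% is taken as the working range.

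**6. False-positive rate.** n = 55, true PFS-6 = 16%, success if the lower 90% limit is at least 16%. With m = n - k and p = x/m:
- plain limit: p - z*sqrt(p(1-p)/m)
- log-log limit: p^exp(z*s), with s = sqrt((1-p)/(p*m))/|ln p|

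The rate is the sum over k of Binomial(k; 55, f) x P(X at least r_m), where X is Binomial(m, 0.16/(1-f)) and r_m is the smallest count that succeeds.

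| f | Log-log | Plain |
|---|---|---|
| 0 | 4.8% | 2.3% |
| 2% | 4.9% | 3.9% |
| 5% | 5.8% | 4.8% |
| 10% | 8.5% | 6.5% |

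The protocol does not name the interval, so both are shown. The jump in the plain column from f = 0 to 2% is largely discreteness. At m = 55 success needs 15 progression-free subjects (14 give a limit of 15.8%). At m = 54, 14 suffice: 0.259 - 1.645 x sqrt(0.259 x 0.741/54) = 0.161.

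**7. One decision.** Suppose 13 of 55 subjects are progression-free at 6 months.
- All failures counted: 13/55 = 23.6%, lower limit 14.9% (log-log) or 14.2% (plain). Negative.
- Four unscanned failures censored on Day 1: 13/51 = 25.5%, log-log limit 16.1%. Positive.
- Six censored: 13/49 = 26.5%, plain limit 16.2%. Positive on the plain interval too.

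**The case against.** The best defence is that the third PFS sentence is a sub-case of the second. The second sets the censoring date at the last tumor assessment for living, progression-free subjects; the third supplies a date when no such assessment exists. On that reading an early death is an event and nothing is inflated. The reading is reasonable, and a reader should not infer that the protocol has settled that deaths are censored: the event sentence and the alive condition say otherwise. But the third sentence does not say it is a sub-case, and identical wording serves TTP, where death is not an event. What stands is that this is a contradiction in the text. Section 7.1 leaves details of endpoint analyses to the SAP, but an SAP that counted these deaths would depart from the literal sentence.

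It is also fair that clinical progression is partly covered. Section 5.3.7 bases assessments on Appendix 4, and the discontinuation visit calls for an MRI. This limits f to subjects who also miss that scan; it does not cover sudden deaths or subjects too ill to attend.

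Two further inferences go too far.
- An exponential curve with PFS-6 of 16% puts 1 - 0.16^(42/182.6) = 34% of subjects past a PFS event by week 6. That is not an estimate of f, because the Cycle 3 and discontinuation scans would capture most of those progressions.
- A reader might also want the evaluable population redefined: "The evaluable population will include all subjects who received at least 1 dose of MEDI-575 and had at least 1 post-baseline disease assessment". That population is secondary to ITT. It requires a disease assessment, and Section 5.2.6.3 lists examination and performance status alongside MRI under disease evaluation, so it does not clearly require a scan. Changing it would be a preference.

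**Conclusion.** The point holds as an internal contradiction in the only PFS definition available for the primary endpoint, with a one-directional effect if the last sentence is followed literally. The size rests on an assumed f, on follow-up to 6 months being otherwise complete, and on the interval chosen. At f = 2% the shift is 0.3 points and the log-log false-positive rate barely moves. Under a plain interval the rate stays below 5% up to f = 5%. Near f = 10% the effect is material: 1.8 points at the null, and a false-positive rate above the nominal one-sided 5% under either interval. Four unscanned failures can reverse the conclusion in a borderline result under a log-log interval. The documents do not show that f will be high, nor that the sponsor intends to censor deaths. Because the ambiguity bears directly on the success criterion, it should be resolved before analysis.

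**What to change.** In Section 7.3.2.1, restrict Day 1 censoring of PFS to subjects who are alive, have no RANO progression (including the clinical progression recognised in Appendix 4) and have no post-baseline tumor assessment. State that an unscanned death is a PFS event on the date of death, and that a documented clinical progression is a PFS event on its date. State in Section 7.3.1 that PFS-6 uses this definition.

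Align the TTP sentence for documented clinical progression only; death is not a TTP event. The evaluable population can stay as it is.

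The cost is a few sentences in the protocol, carried into the SAP. No new data are needed, because survival status and disease status are already collected, and the sample size does not change.
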